	
 3. Vital signs; 4. Medical and surgical history; 5. Demographic information; 6. Details of injury; 7. Severity of injury; 8. Medications; 9. Physical exam with range of motion (ROM) of the target limb; 10. BMI; 11. Urine pregnancy test for Women of Child Bearing Potential (WOCBP); 12. Blood analysis; 13. Completion of augmented PROs, including: NRS, IKDC, Lysholm, TEGNER, WOMAC and SF-12; 14. A radiograph of the target knee will be performed to confirm the presence of Kellgren-Lawrence grade II-IV OA; 15. The patients' medical record will be reviewed, and the subject will be interviewed to determine if inclusion/exclusion criteria are met; 16. Randomization. 
Patients who have met all eligibility criteria will be assigned, 1:1 via block randomization, to one of the two blinded study groups.
 
Visit 2 (Baseline) (Within 3 months of Visit 1)
 
Some procedures performed in this visit may be performed in Visit 1 provided that Informed Consent has been signed.
 
 1. Urine pregnancy test for Women of Child Bearing Potential (WOCBP) 2. Quantitative MRI; 3. Kinematic movement; 4. Assessment of muscle strength, isokinetic dynamometry; 5. Functional performance testing.
--	---

	
After randomization is performed, a Study Team member will then inform the Vail Hospital pharmacist of the subject's assigned randomization code the study medication will be obtained. The subject will take the first dose of study medication at the clinic.
 
Subjects will be instructed to self-medicate for day 2 followed by 28 days off. They will be instructed to begin a second course of treatment for two consecutive days (days 31 and 32).
 
Subjects will be reminded at Visit 3 in-person and over the phone 2-4 days prior to the last dosing of study medication about their upcoming dosing. If applicable, they will also be reminded to withhold current medications as instructed by the PI.
 
A Medication Log recording medication administration will be provided to the subject with instructions to complete during the period of administration.

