7.4.4 Intermittent Dosing Schedule

Senolytic drugs (including FIS) can effectively kill senescent cells with one to two doses given systemically¹. We believe that allowing two week breaks between dosing will be more tolerable to patients as compared to sustained dosing, therefore minimizing protocol deviations.

We further believe that intermittent dosing may minimize the occurrence of potential drug-drug interactions and hopefully decreasing the frequency or magnitude of any potential side effects further discussed in **Section 13.1** of this protocol.

7.4.5 2 Month Duration

We have chosen a 2-month (32 days) dose duration based upon pre-clinical studies reviewed in **Section 5.3** of this protocol. Several studies have treated mice with our proposed dose and more, for over two months (equivalent of ~20 years in the human lifespan). Considering the comparative life span between the mouse model and of humans, we believe that a 2-month duration is a safe and effective length of time.

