9.1.2 Exclusion Criteria

Subjects will be excluded if any of the following criteria are met:

1. Females who are nursing, pregnant or planning to become pregnant during the duration of study drug dosing;
2. Males who do not wish to abstain from sex or use contraceptive protection during study drug dosing and for 2 weeks after the last dose;
3. Subjects who do not have the capacity to consent themselves;
4. Subjects who are unable to tolerate oral medication;
5. Subjects having previously undergone any of the following treatments in the stated time window:
 - a. Surgery on the Study Knee in the past 6 months;
 - b. Partial or complete joint replacement in the study knee. Partial or complete joint replacement in the contralateral knee is acceptable as long as the surgery was performed at least 6 months prior to enrollment and the operative knee is asymptomatic;

-
- c. Patients who have undergone arthroscopic surgery (including microfracture and meniscectomy) on the Study Knee in the last 2 years prior to the Screening visit or are anticipated to have arthroscopic surgery on either knee at any time during the study period;
 - d. Steroid injection, including extended-release corticosteroid (e.g., Zilretta®) within the last 5 months;
 - e. Biologic (platelet-rich plasma, bone marrow, adipose tissue/cells) or hyaluronic acid injection into the Study Knee in the past 6 months;
6. Subjects with any of the following drug/medication statuses:
- a. Currently taking Losartan;
 - b. Opioid analgesics taken in the past 8 weeks and are not willing to discontinue these medications through the duration of the study;
 - c. Senolytic agents taken within the past 6 months and are not willing to discontinue these medications through the duration of the study, including: Fisetin, Quercetin, Luteolin, Dasatinib, Piperlongumine, or Navitoclax;
 - d. Drugs that induce significant cellular stress and are not willing to discontinue these medications through the duration of the study, including alkylating agents, anthracyclines, platins, other chemotherapy drugs;
 - e. **Subjects taking the following other drugs if they cannot be held (per the Principal Investigator) for at least 2 days before and during administration of Fisetin:** cyclosporine, tacrolimus, repaglinide, and bosentan.;
7. Subjects with any of the following disease statuses:

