10.0 Study Visits

A full Study Schemata is provided in **Section 23.1** of this document.

Visit 1 (Screening/Enrollment)

At the first patient visit, the following procedures will be performed:

1. Full explanation of the clinical study, execution of Informed Consent, copy of signed informed consent sent home with patient;
2. Subject will be assigned a deidentified study number;
3. Vital signs;
4. Medical and surgical history;
5. Demographic information;
6. Details of injury;
7. Severity of injury;
8. Medications;
9. Physical exam with ROM of target limb;
10. BMI;
11. Urine pregnancy test for pre-menopausal women;
12. Blood analysis;
13. A radiograph of the target knee will be performed to confirm the presence of Kellgren-Lawrence grade II-IV OA;
14. The patients' record will be reviewed, and the subject will be interviewed to determine if the eligibility criteria are met;
15. Randomization.

Patients who have met all eligibility criteria will be assigned, 1:1 via block randomization, to one of the two blinded study groups.

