10.1 Visit 2 (Baseline): (Within 3 months of Visit 1)

Some procedures performed in this visit may be performed in Visit 1 provided that Informed Consent has been signed.

1. Urine pregnancy test for Women of Child Bearing Potential (WOCBP)

-
2. Quantitative MRI;
 3. Kinematic movement;
 4. Assessment of muscle strength, isokinetic dynamometry;
 5. Functional performance testing.

After randomization is performed, a Study Team member will then inform the Vail Hospital pharmacist of the subject's assigned randomization code, and obtain study medication. Subjects will take their first dose of study medication at the clinic.

Subjects will be instructed to self-medicate for day 2 followed by 28 days off. A second course will be taken for two consecutive days (days 31 and 32).

A Medication Log recording medication administration will be provided to the subject with instructions to complete during the period of administration.

10.2 Visit 3: Two Weeks after first dose of Fisetin or Placebo (+/- 2 days)

All subjects will return to the study site 2-weeks from the subject's last dose of Fisetin or placebo. The following procedures will be performed:

1. Blood Analysis.

10.3 Visit 4: Two Weeks from the Subject's Last Dose of Fisetin or Placebo (+/- 10 days)

All subjects will return to the study site two-weeks from the subject's last dose of Fisetin (FIS) or placebo. The following procedures will be performed:

1. Vital signs;
2. Medical and surgical history;
3. Physical exam with ROM of target limb;
4. Blood analysis;
5. Medications;

-
6. Completion of augmented PROs, including: NRS, IKDC, Lysholm, TEGNER, WOMAC and SF-12;
 7. Protocol deviation assessment;
 8. Adverse event assessment.

10.4 Visit 5: Six Months from the Subject's First Dose of Fisetin or Placebo (+/- 4 weeks)

1. Vital signs;
2. Medical and surgical history;
3. Physical exam with ROM of target limb(s);
4. Blood analysis;
5. Completion of augmented PROs, including: NRS, IKDC, Lysholm, TEGNER, WOMAC and SF-12;
6. Medications;
7. Protocol deviation assessment;
8. Adverse event assessment;
9. Quantitative MRI;
10. Lower-extremity kinematic testing with video-motion analysis;
11. Isokinetic dynamometry testing;
12. Functional performance testing.

10.5 Visit 6: 12 Months following First Dose of Study Medication (+/- 4 weeks)

All procedures performed in Visit 5 will be repeated.

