13.1 Associated with Fisetin Administration

Based upon the review of the published literature, pre-clinical data and available clinical data, we do not anticipate the occurrence of serious adverse events related to the prescribed regimen of Fisetin (FIS) in this study. However, potential side effects include the following:

- Reduced appetite,
- Altered activity,
- Nausea,
- Dry mouth,
- Diarrhea,
- Vomiting,
- Fatigue.
- There have been positive findings with Fisetin in the Ames and micronucleus assays.

In addition, FIS has been demonstrated to have inhibitory activity of cytochrome P450, and to have adverse interaction with caffeine, tobacco/nicotine consumption for which we have established exclusion criteria. These are listed in detail in **Section 9.1.2** of this protocol. In addition, a list of possible drug interactions with FIS are provided in **Section 22.4, Appendix D** of this document.

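### Contraception is an eligibility condition for men but not for women of childbearing potential, despite positive genotoxicity assays

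*Combined protocol and SAP*

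**What the plan says.** Exclusion items 1 and 2 treat the sexes differently, in the same words in Section 9.1.2 and in the Synopsis. For women: "Females who are nursing, pregnant or planning to become pregnant during the duration of study drug dosing". For men: "Males who do not wish to abstain from sex or use contraceptive protection during study drug dosing and for 2 weeks after the last dose".

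The plan expects some women of childbearing potential. Entry starts at age 40. Section 10.0 lists, at Visit 1, a "Urine pregnancy test for pre-menopausal women", and Section 10.1 schedules another urine test at Visit 2, where the first dose is taken in clinic. The schedule in Appendix B shows no pregnancy test after Visit 2.

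Section 7.4.1 places dosing on days 1, 2, 31 and 32. Among the risks of the drug, Section 13.1 states: "There have been positive findings with Fisetin in the Ames and micronucleus assays".

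**The concern.** An exclusion for planning a pregnancy addresses intent. It does not address the chance of an unplanned conception in a woman who uses no contraception, and she passes items 1 and 2 as written.

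The plan thought contraception worth requiring of men. A woman who conceives between the two courses would take the second course herself while pregnant, so her exposure would be direct. With positive genotoxicity assays on record, a condition stated for men alone is hard to justify. Section 12.2.6 counts a congenital anomaly or birth defect as a serious outcome, and safety is the primary objective.

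What is at stake is participant protection. No estimate, test or sample-size figure depends on it.

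**Working it through.** The plan has no figure of its own to reproduce here. The check is a comparison of texts plus day counts.

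**1. Contraception or abstinence condition in the eligibility text**

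| Place | Men | Women of childbearing potential |
|---|---|---|
| Section 9.1.2, items 1 and 2 | Yes, dosing plus 2 weeks | None |
| Synopsis, items 1 and 2 | Yes, dosing plus 2 weeks | None |

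The condition appears in 2 of 2 places for men and 0 of 2 for women. No other inclusion or exclusion criterion supplies it.

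**2. Length of the stated conditions**

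- Men: last dose on day 32, plus 14 days, gives day 46. The condition covers days 1 to 46.
- Women: the intention exclusion covers dosing. Section 7.4.5 says "We have chosen a 2-month (32 days) dose duration", so it is read as days 1 to 32, with no period after the last dose.
- Difference in end dates: 46 − 32 = 14 days. This sets a contraception rule against an intention exclusion, so it carries little weight.

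**3. Untested interval before the second course**

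- Last scheduled test: Visit 2, day 1. Second course starts on day 31. 31 − 1 = 30 days.
- Section 10.1 also says: "Some procedures performed in this visit may be performed in Visit 1 provided that Informed Consent has been signed". Footnote 4 of Appendix B repeats this, and neither exempts the pregnancy test. Visit 2 may be up to 3 months after Visit 1, so a test moved forward would leave a longer interval.

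**4. Existing contacts where a repeat test could be placed**

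- Visit 3: day 1 + 14 = day 15, ± 2 days, so days 13 to 17. That is 31 − 17 = 14 to 31 − 13 = 18 days before the second course.
- Reminder call: the Synopsis says "Subjects will be reminded at Visit 3 in-person and over the phone 2-4 days prior to the last dosing of study medication". If the last dosing means day 31, the call falls on days 27 to 29; if it means day 32, on days 28 to 30. That is 31 − 30 = 1 to 31 − 27 = 4 days before the second course.

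**5. Other safeguards for women in the visible text**

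- Item 9 of the exclusions gives the investigator discretion, but it turns on a medical condition, which non-use of contraception is not clearly.
- Section 14.3 allows removal of a subject at risk, but this is discretionary and depends on the investigator knowing of the risk.
- The three calls in Section 10.8 are for dose reminders and adverse events; no pregnancy check is mentioned.

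None of these is a contraception rule or a pregnancy test before days 31 and 32.

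**The case against.** The strongest objection is that the deciding document is unseen. The consent form is Appendix A of this protocol and a natural home for contraception instructions. Inclusion item 2 requires willingness to comply with study procedures, so instructions there could bind every enrolled woman. If so, the point shrinks to where the wording sits. This stands as a limit on the claim, but it does not remove it: screening is done against the eligibility criteria, and those state the condition for one sex only.

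Second, the link to genotoxicity is an inference. Section 13.1 gives one line, with no dose, test system or reproductive data, and the plan never says that the men's rule rests on those assays. That is correct. The risk is not quantified, and the two items are asymmetric rather than contradictory.

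Third, women are not unprotected. Pregnancy, nursing and planned pregnancy are excluded, two urine tests are scheduled, dosing covers only four days, and there is contact at Visit 3 and by telephone. The residual case is an unplanned conception, mainly between courses, in the childbearing part of a population aged 40 to 80. That narrows the gap without closing it.

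Fourth, the 2-week post-dose period is borrowed from the men's rule, for which the plan gives no reason. The timing of the reminder call is stated only in the Synopsis, since Section 10.8 gives none. Both are fair. They bear on the details of the remedy, not on the omission.

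**Conclusion.** The concern holds. Section 9.1.2 and the Synopsis require abstinence or contraception of men on days 1 to 46 and state no such condition for women of childbearing potential. A woman who uses no contraception can be enrolled and dosed again 30 days after her last scheduled pregnancy test.

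This should be corrected, as a participant-safety point. Confidence is medium because the consent form could not be checked. The conclusion assumes that item 1 covers the whole 32-day dosing period and that the Visit 2 test is done on day 1. The number of women affected cannot be estimated from the documents.

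**What to change.** Amend item 1 in Section 9.1.2 and the Synopsis so that women of childbearing potential must agree to abstain or use contraception during dosing (days 1 to 32) and for a period afterwards at least matching the men's 2 weeks (to day 46). The clinical team and the medical monitor should set the final length. Check the consent form for existing wording and align it.

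Two smaller changes are worth making in the same amendment:

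- State in Section 10.1, the Synopsis and footnote 4 of Appendix B that the Visit 2 urine test is done before the first dose and may not be moved to Visit 1.
- If the clinical team wants a repeat test, place it just before day 31, for example a home urine test confirmed at the reminder call, with the timing of that call written into Section 10.8. Visit 3 would be 14 to 18 days too early. A repeat test would miss very recent conceptions, so it supplements the contraception condition and does not replace it.

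The cost is eligibility and schedule wording, consent alignment, and at most one extra urine test per woman of childbearing potential. The effect on recruitment is assumed small at ages 40 to 80; the documents give no figure from which to set a range.

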10.0 Study Visits

A full Study Schemata is provided in **Section 23.1** of this document.

Visit 1 (Screening/Enrollment)

At the first patient visit, the following procedures will be performed:

1. Full explanation of the clinical study, execution of Informed Consent, copy of signed informed consent sent home with patient;
2. Subject will be assigned a deidentified study number;
3. Vital signs;
4. Medical and surgical history;
5. Demographic information;
6. Details of injury;
7. Severity of injury;
8. Medications;
9. Physical exam with ROM of target limb;
10. BMI;
11. Urine pregnancy test for pre-menopausal women;
12. Blood analysis;
13. A radiograph of the target knee will be performed to confirm the presence of Kellgren-Lawrence grade II-IV OA;
14. The patients' record will be reviewed, and the subject will be interviewed to determine if the eligibility criteria are met;
15. Randomization.

Patients who have met all eligibility criteria will be assigned, 1:1 via block randomization, to one of the two blinded study groups.

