9.1 Enrollment Criteria

9.1.1 Inclusion Criteria

Subjects will be included if all of the following criteria are met:

1. Are male or female, ages 40-80;
2. Are willing to comply with all study related procedures and assessments;
3. Are ambulatory as defined by ability to complete functional performance testing;
4. Radiographic evidence of Kellgren-Lawrence grade II-IV osteoarthritis in one or both knees;
5. Scores 4-10 on the Numerical Rating Scale (NRS) for pain;
6. Stable dose of screening/baseline medications for at least 2 months prior to the anticipated date of study drug dosing.

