15.4 General Data Handling, Analysis, and Reporting Strategy

Intent-to-treat analysis will be performed.

Baseline covariates will be summarized and reported in a table, stratified by group. This is a randomized trial, thus the expected population group differences with respect to baseline covariates are zero by definition. For this reason, no statistical comparisons will be performed to test for differences in baseline covariates between groups.

Whenever applicable, assessment of endpoints that are measured at serial time points will be analyzed using methods that account for this repeated measure structure. Listwise deletion in response to missing data points and categorization/dichotomization of continuous measurements will be avoided to every extent possible.

Summary statistics will be reported as group medians with quartiles or extrema. Meanwhile estimates calculated for statistical inference will be reported with $(1-\alpha)\%$ confidence intervals. Model fit and satisfactorily meeting model assumptions will be assessed for all multivariable regression and linear mixed-effects models using residual analysis.

The Statistical Computing Language R will be used to produce all analyses and plots.

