22.2 Appendix B – Study Schemata

Visit Type	Screening	Baseline (4)	Emailed patient questionnaires	Safety Blood Draw	Phone Calls	Study Visit	Study Visit	Study Visit	Emailed patient questionnaires	Unscheduled
Clinic Visit Number	1	2		3		4	5	6		
Visit Date			Every 3 days for 6 wks after first dose of study drug and weekly for 6 wks thereafter	2 weeks after first dose of study drug	3 times after first dose of study drug	2 weeks after last dose of study drug	6 months after first dose of study drug	12 months from first dose of study drug	18 months after first dose of study drug	As needed for AEs/SAEs
Acceptable Visit Window		within 3 months of screening	± 1 day	± 2 days		± 10 days	± 4 weeks	± 4 weeks	± 4 weeks	N/A
Procedures & Assessments										
Informed Consent (1)	X									
Randomization (Placebo or Fisetin) (5)	X	X								
Medical/Surgical History & Demographics	X									
Physical Exam with Range of Motion of Study Knee	X					X	X	X		X
Vitals	X	X				X	X	X		X
BMI	X									
Record concomitant medications & supplements	X	X				X	X	X		X
Blood Draw (6)	X	X		X		X	X	X		X
Urine pregnancy test for WOCBP (2)	X	X								
PRO questionnaires			X			X	X	X	X	
Radiograph of Study Knee (3)	X									
Quantitative MRI		X					X	X		
Biomotion tests (functional performance, joint range of motion, muscle strength, video motion analysis)	X	X					X	X		
Dispense study drug		X								
Provide study drug diary		X								
Return study drug and diary						X				
Review and Assess AEs and SAEs				X	X	X	X	X		X

FOOTNOTES:

(1) Informed consent must be signed by the patient prior to ANY research-related procedures. The informed consent document can only be signed by the study PI and/or the treating clinician (MD/NP/PA) who is on the protocol.
(2) WOCBP = Women of Child Bearing Potential
(3) To confirm the presence of Kellgren-Lawrence grade II-IV OA.
(4) Procedures at Baseline may be performed at the Screening Visit after the Informed Consent Form (ICF) is signed.
(5) Randomization can occur at Screening or Baseline as long as the ICF has been signed and patient eligibility in the study is confirmed.
(6) If the Baseline visit occurs greater than 3 months after the Screening Visit, blood should be collected again for safety purposes.

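### Randomization is permitted at Visit 1, up to 3 months before baseline testing and first dose, so the intent-to-treat set may hold undosed subjects without MRI, strength or functional baselines

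*Combined protocol and SAP*

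**What the plan says.** **When allocation happens.** Section 10.0 ends its Visit 1 list with "15. Randomization" and adds: "Patients who have met all eligibility criteria will be assigned, 1:1 via block randomization, to one of the two blinded study groups". The Synopsis does the same. Section 15.3 ties the token draw to enrollment, and Visit 1 is titled Screening/Enrollment. Appendix B marks both the Screening and Baseline columns, and its footnote 5 reads: "Randomization can occur at Screening or Baseline as long as the ICF has been signed and patient eligibility in the study is confirmed".

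**What comes later.** Section 10.1 sets Visit 2 within 3 months of Visit 1. It holds the second pregnancy test, quantitative MRI, kinematics, isokinetic strength, functional testing and the first dose. Appendix B footnote 4 lets this gap shrink to nothing: "Procedures at Baseline may be performed at the Screening Visit after the Informed Consent Form (ICF) is signed". Footnote 6 foresees it growing past the window: "If the Baseline visit occurs greater than 3 months after the Screening Visit, blood should be collected again for safety purposes".

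**How eligibility is checked.** In Section 10.0 the Visit 1 check is a review of the patient's record and an interview. Blood is drawn at the same visit, and Section 9.1.2 has exclusions on bilirubin, eGFR and HbA1c. Inclusion criterion 3 in Section 9.1.1 is "Are ambulatory as defined by ability to complete functional performance testing".

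**Analysis set.** Section 15.4 gives one sentence: "Intent-to-treat analysis will be performed". Section 15 defines no safety or dosed set and gives no rule for subjects who are randomized but never dosed.

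**The concern.** Anything that happens between allocation and first dose happens to a randomized subject. With up to 3 months in between, a subject may withdraw, change medication, or have a positive Visit 2 pregnancy test. A late laboratory result is a further possibility, because no wait for results is written down.

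Such a subject uses one of the eight tokens in a block and belongs to the intent-to-treat set under any ordinary reading. The subject may nevertheless have no drug and no MRI, strength or functional baseline. The data that the primary endpoint and follow-up need are defined by reference to dosing, so there is nothing to anchor that subject's record. Each such loss also draws on the 20% allowance in Section 15.6 before treatment starts. The sponsor can avoid these losses, unlike dropout after dosing.

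**Working it through.** **1. Does the text allow a gap?** Yes.
- Allocation: Visit 1 (Synopsis, 10.0); at enrollment (15.3); Visit 1 or Visit 2 (Appendix B footnote 5).
- Baseline MRI, strength and function: Visit 2 (10.1, 11.6.2, 11.7, 11.9). Appendix B also marks the biomotion tests at Screening, which disagrees with 10.0 and 11.7.
- First dose: Visit 2 (10.1).
- Permitted gap: 0 to 3 months, with a longer one anticipated by footnote 6.

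**2. What happens to a randomized, never-dosed subject?**
- Adverse events (primary endpoint): Section 12.1 counts them from administration of Study Medication, so there is no start point.
- Visits 3 to 6 and the 18-month contact: timed from the first or last dose (10.2 to 10.6), so there are no due dates.
- Time to conversion: starts at day one of medication (8.2.2), so there is no origin.
- MRI, strength and function: no baseline if Visit 2 did not take place.

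**3. The plan's own sample size.** Inputs from Section 15.6: standardized difference d = 0.73, two-sided alpha 0.05, power 80%, 30 per group, plus 6 per group for 20% dropout.
- Normal approximation: n = 2(1.960 + 0.842)²/0.73² = 29.5, so 30 per group. The stated figure is reproduced.
- Exact two-sample t-test: 30.45, so 31 per group. Power at 30 is 79.4%.
- After 20% dropout, 36 per group leaves 36 × 0.8 = 28.8 evaluable. This is below 30 because the plan inflates by 30 × 1.2 rather than 30/0.8 = 37.5, or 38.

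**4. Illustration of pre-dose loss.** Assumption, not in the documents: a fraction f of each group is lost before dosing, contributes no outcome MRI, and is lost on top of the 20% dropout. Evaluable m = N × 0.8 × (1 − f). Power is from the noncentral t distribution with noncentrality 0.73 × √(m/2) and 2m − 2 degrees of freedom; m is not rounded.

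| N per group | f | m | Noncentrality | Power |
|---|---|---|---|---|
| 36 | 0 | 28.8 | 2.770 | 77.7% |
| 36 | 5% | 27.36 | 2.700 | 75.5% |
| 36 | 10% | 25.92 | 2.628 | 73.1% |
| 50 | 0 | 40 | 3.265 | 89.7% |
| 50 | 5% | 38 | 3.182 | 88.1% |
| 50 | 10% | 36 | 3.097 | 86.3% |

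The two values of N are both in the plan: 36 per group in Sections 6.0 and 15.6, and 50 per group at the cap of 100 in Section 7.5.1. At N = 36, f of 5% or 10% is 1.8 or 3.6 subjects per group.

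**The case against.** The plan does gate allocation on eligibility. Section 10.0 and footnote 5 both require it to be established first, and Section 6.0 describes screening and blood analyses before assignment. Footnotes 4 and 5 also let a site do everything at one visit or randomize at Baseline. All of that stands, and it rules out several stronger readings.

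- A reader might infer that subjects are randomized before laboratory results exist. The documents do not say so: a numbered list does not fix the order within a visit, and no turnaround time is given. They only fail to state a wait.
- A reader might infer that functional ability, MRI suitability and stable medication cannot be known until Visit 2. Appendix B marks functional testing at Screening. Exclusion 8 rests on BMI, implants and claustrophobia, which can largely be judged at Visit 1. Inclusion 6 refers to an anticipated dosing date, so it is meant to be judged ahead.
- A reader might say such subjects have no baselines at all. Range of motion and blood are taken at Visit 1, and the Synopsis adds patient-reported outcomes there. The planned Welch tests on function use no baseline, and the MRI mixed model can use a subject whose baseline is missing.
- A reader might dilute the effect instead: at 10% never dosed, 0.73 × 0.9 = 0.657, with power at 30 per group falling from 79.4% to 70.6%. That needs undosed subjects to return for outcome MRIs, although those visits are timed from the first dose. The same subjects cannot also use up the loss allowance. Loss of data is the likelier case and costs less.

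The eligibility gate does not cover withdrawal, or ineligibility that arises after allocation. The Visit 2 pregnancy test can follow randomization by months.

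**Conclusion.** The concern holds in a limited form. The documents permit, but do not require, allocation up to 3 months before baseline testing and dosing, and they disagree about when it occurs. Undosed subjects without MRI, strength or functional baselines may therefore enter an intent-to-treat set that has no rule for them. It does not follow that ineligible subjects will be included.

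The power cost is modest: about 2 to 5 percentage points at 36 per group for assumed pre-dose losses of 5% to 10%, and power remains at 86% or more at 50 per group. Those figures rest on assumed rates and concern T1rho, a secondary endpoint. For the primary endpoint the problem is one of definition: adverse events have no time origin in a subject who was never dosed. If the blinding in Sections 6.1 and 15.3 holds, pre-dose loss should not depend on group, so the expected harm is lost precision and unusable records rather than bias.

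**What to change.** Reconcile the Synopsis, Section 10.0, Section 15.3 and Appendix B (Screening column and footnote 5) on one rule: the token is drawn at the Baseline/dosing visit, after laboratory and other eligibility results are confirmed and the baseline MRI and functional tests are complete, and immediately before the first dose. If baseline procedures are done at the Screening visit, the same order applies. In Section 15.3, replace enrollment as the trigger for the draw.

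A few subjects could still be allocated and not dosed, so Section 15.4 should also say who is in the intent-to-treat set and who is in the safety set.

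The cost is protocol wording, with no added visit: the first dose is already taken in clinic at Visit 2, and Section 10.1 already has the pharmacist informed of the randomization code there. The one practical burden is that the pharmacy must dispense on the day of the draw.
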